5. STUDY DESIGN

This is a Phase 3, Randomized Control Trial, Multi centre, Single-blind, and Parallel group of 6 ± 1 days duration of data collection after topical application to compare the efficacy and safety of standard treatment of musculoskeletal pain in adult populations.

Justification :

- Phase 3 (Confirmatory study)
The study is conducted to demonstrate whether or not a product offers a treatment benefit to adult participants with musculoskeletal pain between test drug (Piroxicam plus Counterirritant) and commonly used NSAID topical products, Piroxicam gel, Diclofenac gel
- Randomized Control Trial (RCT)
Participants are randomly assigned to different treatment or control groups to minimize bias and allow for causal inference.
- Multi centre
The study will be conducted in 2 sites
- Single-blind
To keep this study maintain the integrity of the data, the investigational product will be given a white sticker to cover all over the tube of investigational products. On top of the tube, there is a study label with unique code to differentiate the test drug and comparator drug. With this procedure, participants will not know which products that assigned to them. Therefore participants can be blinded.
- Parallel

The study in which two groups of participants receive Piroxicam plus Counterirritant gel or Piroxicam gel, or Diclofenac gel. Participants are assigned to one of the treatment arms at the beginning of the trial and continue in that arm throughout the length of the trial. Assignment to a group usually is randomized.

5.1 Primary End-Point:

The primary end-point is the difference of musculoskeletal pain reduction ≥ 3 scores, of the response to treatment that can be seen through Brief Pain Inventory (BPI) scores.

Justification:

- The Brief Pain Inventory (BPI) scores.

It is a medical questionnaire that is used to assess pain. It has also been validated for pain assessment chronicle. There are 9 questions related to the pain experienced by the participants. The pain assessment will be given in the form of a score, namely a score of 0 - 10.

Score 0 : No Pain

Score 1 – 3 : Mild Pain

Score 4 – 6 : Moderate Pain

Score 7 – 10 : Severe Pain

The difference BPI scale ≥ 3 , from initial scale of pain to the end of treatment will be captured as the primary efficacy endpoint.

The selection of difference more than equal to 3 was chosen because if the participant has moderate pain at the beginning of the treatment, then at the end of the treatment there is a decrease in pain to mild pain. This can be seen that the treatment is effective in dealing with musculoskeletal pain.

5.2 Secondary End-Point:

- 1) In data related to safety assessment, the number of participants who experienced adverse events (including serious adverse events) with each symptom present will be recorded and causality of adverse events and serious adverse events assessed with the help of Naranjo's algorithm

Justification:

At the 1st visit, participants will bring home Participant's Diary. Participants need to fill in if they experienced with others symptoms after get the treatment. Also they need to file the rescue medication that they consume during the study timeline. On the 2nd visit and last visit the Investigator will ask about the diary and confirmed the symptoms and medication. When there is safety report, the Investigator will fill in the Safety Form from BPOM RI (Form Kuning MESO) and assess the safety events with the help of Naranjo's algorithm.

The type of symptoms and the number of participants who have symptoms and including side effects will be recorded and become data related to product safety.

- 2) Investigator Assessment on Participants motions, through Range of Motion (ROM) and Muscle test.

Justification:

One of the symptoms that must be assessed when there is musculoskeletal pain is the range of motion and muscle movement to perform an activity. Therefore, an assessment for the examination of the range of motion and muscle strength carried out by the examining doctor is needed to determine the effect of the treatment carried out in the success of performing the activity.

The effectiveness of the treatment will be seen from the progress in the range of motion that can be performed by the participant at the end of the treatment compared to the beginning of the treatment according to scientific standards.

Range of motion (ROM) or motion arc in this study will be measured using a universal goniometer following standardized procedures to ensure accuracy and reproducibility. Each joint will be assessed in a consistent anatomical position—either supine, seated, or standing—depending on the specific joint involved (e.g., seated for elbow, supine for knee). The Principal Investigator or Sub-Investigator will perform three consecutive measurements for each motion (e.g., flexion, extension), and the average value will be recorded. Key movements assessed will include knee flexion-extension, ankle dorsiflexion-plantarflexion, elbow flexion-extension, and lumbar spine flexion or fingertip-to-floor distance for back pain. The same assessor will conduct all measurements at each time point to minimize inter-rater variability. Any limitations due to pain, guarding, or compensatory movements will be noted. ROM data will be recorded on standardized forms and used to evaluate treatment effectiveness by comparing baseline to post-treatment values against established minimal clinically important difference (MCID) thresholds.

In this study, the minimal clinically important difference (MCID) for joint range of motion (ROM) will be used to define clinically meaningful improvements in mobility following treatment. Based on validated references, the MCID values applied are $\geq 10^\circ$ for knee flexion/extension (Mizner et al., 2005) and elbow flexion-extension arc (Picha et al., 2020), $\geq 5^\circ$ for ankle dorsiflexion/plantarflexion (Cleland et al., 2013), and either $\geq 10\%$ change or ≥ 5 cm improvement for lumbar spine mobility, depending on the measurement method used (Stratford et al., 1994). These thresholds represent the minimum degree of change perceived as beneficial by patients and are appropriate benchmarks for evaluating functional recovery in musculoskeletal pain conditions.

- 3) Assessment to investigate scales on thermal sensation, thermal comfort, and thermal acceptance using ASHRAE 7-point scale questionnaire and completed with time starting the thermal sensation.

Definition:

Thermal comfort is the condition of mind that expresses satisfaction with the thermal environment and is assessed by subjective evaluation.

Thermal sensation is assessed to determine whether a specific thermal condition can be considered comfortable or not. The most prominent scale used for the assessment of thermal sensation is the ASHRAE 7-point scale, which consists of seven verbal anchors: “cold”, “cool”, “slightly cool”, “neutral”, “slightly warm”, “warm”, and “hot”.

Thermal acceptance, refers to the degree to which a temperature range or condition is considered acceptable or tolerable by individuals.

The number of thermal sensations felt related to the product will be the result related to the participant's acceptance of the sensation.

- 4) Assessment to investigate the disappearance time of musculoskeletal pain (in days).

Definition:

To know the medication given is effective or not, we need to evaluate the musculoskeletal pain score. One of the result that can be seen is the disappearance time of musculoskeletal pain.

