A study that conducted in 1995, with its title “The study of efficacy and safety of anti inflammatory and analgesic cream in the treatment of musculoskeletal pain” described that the standard piroxicam gel 0.5 % versus the test drug, piroxicam and analgesic cream containing methylsalicylate, eugenol and menthol are equally effective and well tolerated in the treatment of musculoskeletal pain. It was interesting to note that most of patients prefer to have the warm feeling after application as it indicates that the medication was working.

Another study that conducted in 1995, with its title “A double-blind randomized study to evaluate the safety and effectiveness of 0.5% Piroxicam gel compared to Counterpain Plus (combination of 0.5% piroxicam gel, 10% methyl salicylate, 5.4% menthol and 1.36% eugenol) in patients with mild osteoarthritis. As conclusion that both Counterpain Plus and Piroxicam gel are equally effective in gradual relief of the knee joint pain that assessed by Visual Analog Scale or Verbal Rating Scale. Both also equally effective help restore the patient’s functional ability.

The last study that executed in 1995 with its title “Comparative study of the clinical effects of Counterpain Plus and Feldene Gel on knee arthrosis”, found that there was no difference between the terms of biographic data, stage of degeneration, Moberg’s functional scores and severity of pain between the groups at pre-trial and the end of the study. Counterpain Plus and Feldene gel have comparable clinical effects on the treatment of knee arthrosis.

In 2009, Taisho Pharmaceutical Holdings acquired the commercial rights of Counterpain in Indonesia. The distribution permit for the Counterpain® PXM product was transferred to PT Taisho Pharmaceutical Indonesia thereafter. Counterpain® PXM as a topical non-steroid anti inflammation drugs (NSAID) Plus Counterirritant such as methyl salicylate, eugenol and menthol, can be used to help relieve musculoskeletal pain and inflammation such as osteoarthritis, acute post-traumatic disorders: tendinitis, tenosynovitis, periarthritis, strain, sprain, muscle tense and low back pain, this indication is approved by BPOM RI in 2011.

There are no recent clinical studies in 2000 onwards that examine the efficacy of Piroxicam plus Counterirritant gel in the treatment of musculoskeletal pain compare with others topical NSAIDs such as Diclofenac gel or Ketoprofen gel.

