6.8.1 Test Drug : Counterpain® PXM

- Active Ingredients : Piroxicam plus Counterirritant (Methyl Salicylate, Eugenol and Menthol)
- Dose :
Adults : Refer to product's leaflet as follow: no occlusive dress should be employed. Apply gel to the affected area three times daily leaving no residual material on the skin. 1 gram of gel (~ 3 cm) applied to the affected area.

The affected areas are:

- The arms: hand, wrist, elbow, shoulder sinistra or dextra
- The legs: feet, ankle, knee sinistra or dextra
- Upper back or Lower back

3 times daily means:

- application one time in morning (06.00 – 11.00),
- one time in afternoon (11.01 – 17.00),
- one time in evening (17.01 – 23.00).

Application of gel will use dosing cards that provided in this clinical study.

- Method of administration: external use only.
- Every visit, participants will get 2 tubes and in total are 6 tubes for 6 ± 1 days application.

Justification:

The dosage for use refers to the Counterpain® PXM leaflet which has been approved by BPOM RI.

Refer to Counterpain® PXM data that 1 gram equal to 3 cm.

Counterpain PXM dalam gram	Setara dengan ukuran (cm)	Setara dengan assay Piroxicam (mg)	Kandungan zat Counterirritant didalamnya		
			Methyl Salicylate	Menthol	Eugenol
1 gram Counterpain PXM	3 cm	Mengandung Piroxicam 4.7 - 5.1 mg	Methyl Salicylate 97.2 - 119.17 mg	Menthol 48.5 - 55.9 mg	Eugenol 12.5 - 14.7 mg

1. 1 GRAM

[figure not shown]

Foto ukuran dalam cm yang setara dengan 1 gram Counterpain PXM

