6.8.2 Comparator Drug : Hotin® DCL

- Active Ingredients : Diclofenac Diethylamine 11.6 mg (Diclofenac Sodium 10 mg)
- Dose : Refer to the product's leaflet : no occlusive dress should be employed. Apply the required amount of cream on the affected area three times a day and rub gently. The amount of cream needed depends on the extent of the painful area. The affected area are :

- In the arms: hand, wrist, elbow, shoulder sinistra or dextra
- In the legs: feet, ankle, knee sinistra or dextra
- Upper back or Lower back

3 times daily means :

- application one time in morning (06.00 – 11.00),
- one time in afternoon (11.01 – 17.00),
- one time in evening (17.01 – 23.00).

Application of gel will use dosing card that provided in this clinical study.

- Method of administration: external use only.
- Every visit, participants will get 2 tubes and in total are 6 tubes for 6 ± 1 days application

Justification:

The dosage for use refers to the HOTIN DCL® leaflet which has been approved by BPOM RI

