6.9 Study Drugs Labelling

A label is needed for the study drug used.

Investigational products will be given to Participants in tube only, no individual box.

All Investigational Products tubes will be covered by white sticker, leaving only the tip of the tube containing the batch number and expiration date information. On top of the white sticker will be a study drug label that have specific code and number.

Below is the labelling process for investigational products :

The packaging label from investigational products will be covered by a white secured sticker. Only the bottom side (tail) which contains the batch number information is left open.

Clinical study label will be put on the top of white sticker.

PRODUK INVESTIGASIONAL NO. BATCH : 4M3101 TGL KADALUARSA : Dec 27 NO. REG : DTL1124403528A1 PENYIMPANAN : Simpan dibawah suhu 30° C <small>Dibuat oleh : PT. Taisho Pharmaceutical Indonesia, Tbk</small>	NO. OBAT : C001 NAMA SITE : Klinik Utama Eminence
PRODUK INVESTIGASIONAL NO. BATCH : 4M3101 TGL KADALUARSA : Dec 27 NO. REG : DTL1124403528A1 PENYIMPANAN : Simpan dibawah suhu 30° C <small>Dibuat oleh : PT. Taisho Pharmaceutical Indonesia, Tbk</small>	NO. OBAT : C199 NAMA SITE : St. Carolus Sports Clinic by Eminence

Final label on the tube

Every tube will be numbered with drug number sequentially, as detailed:

Test drug (Yellow sticker)	Comparator drug (Orange Sticker)	Comparator drug (Brown Sticker)
C001	H001	P001
C002	H002	P002
C003	H003	P003
etc. until the last of stock	etc. until the last of stock	etc. until the last of stock

- Initial “C” for study drug and 3 digits number
- Initial “H” for comparator drug and 3 digits number
- Initial “P” for comparator drug and 3 digits number

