6.12 Dispensing, Storage, Management, and Collection Procedures

The Study Drug Handling Manual will be provided and completed to ensure the study drugs are prepared, shipped, stored, dispensed, and returned to comply with regulations.

The Investigational Products will be relabelled in Sponsor Technical Operations Plant Site. After the Sponsor ensures the quality of the product, the study drug will be relabeled, which means that this drug is used explicitly for clinical studies.

The sponsor will deliver the study drug from the Technical Operations plant to each research site by courier, where it can monitor the temperature of the study drug delivery below 30°C.

The Study Coordinator from each research site will ensure the storage of study drugs.

During the study, the distribution of study drug participants will be prescribed by the Investigator based on randomization and dispensed to the participants by the Sports Therapist during the recovery program.

Use GraphPad QuickCalcs (<https://www.graphpad.com/quickcalcs/randomize1/>) to generate a random allocation list, ensuring equal numbers for each treatment group:

- Group A: Piroxicam + Counterirritant
- Group B: Piroxicam
- Group C: Diclofenac

Each eligible participant will be assigned a unique subject ID upon enrollment. The study coordinator will match the subject ID to a treatment group based on the pre-generated list. All tubes will be labeled with a sticker displaying only the randomization code to maintain blinding of both participants and investigators. The tube will then be dispensed to the participant according to the assigned code. Only the investigator will have access to the full randomization list.

At the end of the study period, all study drugs will be returned by the participants to each site. This return process will be assisted by each Study Coordinator. An then be sent to Technical Operations for destruction.

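### Covering and coding the tube does not secure participant blinding: only the test gel lists counterirritants, and participants who may feel them score the primary endpoint

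*Protocol*

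**What the plan says.** Section 5 calls the trial single-blind and describes the masking: "the investigational product will be given a white sticker to cover all over the tube of investigational products", with a coded study label on top. It then concludes: "With this procedure, participants will not know which products that assigned to them. Therefore participants can be blinded".

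The later sections also deal only with the pack. Section 6.9 repeats the covering ("All Investigational Products tubes will be covered by white sticker"), removes the individual box, and sets out labels that differ by arm: yellow, orange or brown stickers, and tube numbers beginning C, H or P. Section 6.12 again relies on the label: "All tubes will be labeled with a sticker displaying only the randomization code to maintain blinding of both participants and investigators". The protocol does not describe matching the gels for smell, texture or skin sensation, and does not ask participants which product they think they received.

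On the products, section 6.8.1 lists piroxicam plus methyl salicylate, eugenol and menthol as active in the test gel. Sections 6.8.2 and 6.8.3 list only diclofenac and only piroxicam for the comparators. Section 2.1, on a 1995 comparison of piroxicam gel with piroxicam plus the same three counterirritants, reports that "most of patients prefer to have the warm feeling after application as it indicates that the medication was working".

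Section 5.2 makes the sensation a secondary endpoint: "Assessment to investigate scales on thermal sensation, thermal comfort, and thermal acceptance using ASHRAE 7-point scale questionnaire", together with its time of onset. Section 7.9.2 has participants complete this (Form 8) at all three visits, and section 7.4.2 compares it between arms. The primary endpoint, the BPI on Form 2, is filled in by the participant (section 7.9.1 and Appendix 1).

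**The concern.** A sticker hides the print on the tube. It does not hide what the gel does on the skin, and the products differ there by their listed active ingredients. The protocol also supplies the route to bias: patients are reported to read warmth as evidence of effect, and the trial directs their attention to warmth at each visit. The same people then score the outcome.

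An equivalence trial is exposed in both directions. If expectation lowers pain scores in the test arm only, it can offset a real deficit and produce a false claim of equivalence. It can also push a gel that is truly equal outside the margin. Either result would be reported as participant-blinded, with no evidence on whether participants had inferred their arm.

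**Working it through.** **Does the conclusion follow from the plan's own facts?**

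1. All the masking described (sections 5, 6.9 and 6.12) concerns the pack.
2. The table in section 6.8.1 gives, per gram of test gel, 97.2 to 119.17 mg methyl salicylate, 48.5 to 55.9 mg menthol and 12.5 to 14.7 mg eugenol. The sums are 158.2 and 189.77 mg, so about 16% to 19% of the gel by weight is counterirritant. Neither comparator lists any.
3. In the comparison behind the warm-feeling remark in section 2.1, only the test product contained counterirritants. Warmth from the test gel is a strong inference from this, though it is not stated.
4. In the visit flow (section 7.7.2), Form 2 is completed before the clinic application. At Visits 2 and 3 this does not protect the score, because by then the gel has been used at home for days, three times daily.

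The premise (the tube is covered) therefore does not give the conclusion (participants are blinded).

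**How much could it matter?** The plan gives no figure for blinding, so there is none to reproduce. The shift below is an assumption.

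Inputs: n = 54 per arm and SD 1.81 (section 6.7); margin ±1.0 with two one-sided tests (section 7.4.2). Section 7.4.2 sets 0.05 unless adjusted and section 6.7 adjusts to 0.0167 for three comparisons, so both are shown as one-sided levels. The 54 is taken as stated. The formula in section 6.7 with its own inputs gives (3.23 × 1.81)² = 34.2, and reaches 54.0 only with the printed 4.059. That is a separate matter.

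- Standard error: 1.81 × √(2/54) = 0.348.
- Equivalence is declared if the observed difference lies within ±(1.0 − z × 0.348). With z = 1.645 this is ±0.427; with z = 2.128 it is ±0.259.
- For expected difference D and half-width h, the probability is Φ((h − D)/0.348) − Φ((−h − D)/0.348).
- A gel truly 1.0 point worse, with shift b in its favour, has D = 1 − b. A truly equal gel has |D| = b.

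Example, b = 0.5 at 0.05: Φ(−0.21) − Φ(−2.66) = 0.417 − 0.004 = 0.413.

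| Assumed shift b | Truly 1.0 worse, 0.05 | Truly 1.0 worse, 0.0167 | Truly equal, 0.05 | Truly equal, 0.0167 |
|---|---|---|---|---|
| 0 | 5.0% | 1.7% | 78.0% | 54.2% |
| 0.25 | 17.7% | 7.7% | 66.8% | 43.8% |
| 0.5 | 41.3% | 23.0% | 41.3% | 23.0% |
| 0.75 | 66.8% | 43.8% | 17.7% | 7.7% |

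Entries are the probability of declaring equivalence for one pairwise comparison. This is a normal approximation, without the gain from baseline adjustment.

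**The case against.** Several points on the other side stand.

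- **A reader might infer that the protocol says the test gel feels warm.** It does not. The remark in section 2.1 names no arm, and the explicit warm sensation earlier in that section belongs to the Counterpain cream variant, not to PXM. Comparator excipients are not described either. The supportable word is likely.
- **A reader might infer that participants will know their arm.** Feeling something is not knowing the allocation, and nothing shown says that participants are told which gel should be felt.
- **A reader might infer that the plan ignores the problem.** It does measure the cue: Form 8 is collected at each visit and compared by arm. What it lacks is a record of what participants conclude from it.
- **The argument has limited reach.** No listed ingredient separates the two comparators by feel, so piroxicam against diclofenac is not affected.
- **The shift has no source in the documents**, and 0.75 is three quarters of the margin. Counterirritants are declared active substances, so part of any sensation-linked relief could be a product effect. The documents cannot separate the two.

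Another 1995 comparison in section 2.1 is titled double-blind, but no evidence is given that its blinding held, so it does not answer the point. None of these objections restores the step from a covered tube to a blinded participant.

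**Conclusion.** The concern holds in a limited form. Section 5 claims a property that the described masking does not secure, for the two comparisons that involve the test gel. The documents support likely recognition by feel. They do not support certain unblinding, or any particular size of bias.

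Under the assumed shifts of 0.25 to 0.75 points, the chance of declaring a gel 1.0 point worse to be equivalent is about 18% to 67% instead of 5%, or 8% to 44% instead of 1.7% at the adjusted level. If the gels are equal, power falls from 78% to between 67% and 18%, or from 54% to between 44% and 8%. These figures rest on 54 per arm, SD 1.81, and the whole shift being bias in the test arm.

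The coloured stickers and the C, H and P codes might be read as proof that the pack itself unblinds participants. The documents do not show that participants hold the key. The codes do mean that the plan cannot claim the tubes look alike.

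**What to change.** 1. In section 5, replace the concluding sentence with a statement that the product name on the tube is covered but the sensory effect of the gel is not masked. Do not add that tube appearance is masked, because sticker colour and code letter differ by arm in section 6.9.
2. The consent pages were not available for this review. If the participant information does not already say so, add a neutral line: any of the gels may or may not be felt on the skin, and this shows neither which gel it is nor whether it works.
3. At Visit 3, after Form 2 is complete, ask which product the participant believes they received and why. Tabulate the answers by arm next to the Form 8 results.
4. Report the equivalence results for the test gel as not assured to be participant-blinded.

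The cost is one form item, one table, possibly one line of information text, and a weaker stated blinding claim. A guess made at the end is partly confounded with perceived relief, so it is descriptive only and does not remove bias. It has to be collected at the time, because it cannot be recovered once participants have finished.

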6.2 Inclusion criteria

- Outpatient in a health care setting.
- Between the ages of 18 - 60 years of either sex.
- Patients diagnosed with musculoskeletal pain as described in the target population.
- Patient can read and understand how to fill out the assessment form and diary.
- Patients gave written consent to participate in the study independently.

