6.7 Sample Size

Assumptions

- Outcome	: Pain score
- Standard deviation (σ)	: 1.81
- Clinically meaningful margin (Δ or δ)	: 1.0
- Power	: 80% ($Z_{1-\beta} = 0.84$)
- Significance level (α)	: 0.05

Reference standard deviation from Kocak AO, Dogruyol S, Akbas I, Menekse TS, Gur STA, Kocak MB, Cekmen B, Orun S, Cakir Z. Comparison of topical capsaicin and topical piroxicam in the treatment of acute trauma-induced pain: A randomized double-blind trial. Am J Emerg Med. 2020 Sep;38(9):1767-1771. doi: 10.1016/j.ajem.2020.05.104. Epub 2020 Jun 2. PMID: 32739846.

For **equivalence trials with 3 groups**, you typically plan for **pairwise equivalence testing**:

- Diclofenac vs. Piroxicam
- Diclofenac vs. PXM plus Counterirritant
- Piroxicam vs. PXM plus Counterirritant

This means you must **adjust α** to account for **multiple comparisons**, commonly using **Bonferroni correction**:

$$\text{Adjusted } \alpha = 0.05 / 3 = 0.0167 \rightarrow Z_{1-\alpha/2} \approx \mathbf{2.39}$$

Sample Size Formula and Calculation

Using the formula for equivalence trials:

$$n = ((Z_{1-\alpha/2} + Z_{1-\beta}) \times \sigma / \Delta)^2$$

Substituting the values:

$$n = ((2.39 + 0.84) \times 1.81 / 1.0)^2$$

$$n = (4.059 \times 1.81)^2 = (7.35)^2 = 54.0$$

Sample size per group (rounded): 54

Total sample size for 3 groups: 162

With 10% dropout:

Total = $162 / (1 - 0.10) \approx 180$ participants

Recommended: 60 participants per group

The clinical study will be recruited in total 180 subjects, which means 60 subjects per arm.

Justification:

- We used the reference from Kocak et al. because: The study used topical piroxicam, which is the main active ingredient in Counterpain PXM. The study was randomized, double-blind, and controlled, and reported the standard deviation of pain scores in full—a parameter that is essential for sample size calculations. To date, we have not found any publications comparing diclofenac gel directly with topical piroxicam, with standard deviations appropriate for use in statistical calculations. So, even though the comparator was capsaicin, this reference was chosen because it is quite representative in terms of pain type and study design.

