7.9.1 Primary Endpoint

The assessment of primary endpoint will be assessed through form 2, Inventerisasi Rasa Nyeri Singkat on 1st Visit, 2nd Visit and 3rd Visit.

The primary end-point is the difference BPI scale ≥ 3 , from initial scale of pain to the end of treatment will be captured as the primary efficacy endpoint.

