7.4.2 Statistical Analysis Plan

The statistical analysis will be performed after data finalization and database lock, following the predefined analysis sets (PPS, FAS, and Safety Analysis Set). All analyses will be conducted using standard statistical software (e.g., SPSS, SAS, or R), with the level of statistical significance set at $p < 0.05$, unless otherwise adjusted.

Efficacy Analysis

- **Primary Endpoint (Pain Score using Brief Pain Inventory):**
 - **Test: Analysis of Covariance (ANCOVA)** adjusting for baseline BPI score

- **Equivalence testing:** Pairwise comparisons using **two one-sided t-tests (TOST)** to assess whether the difference in mean change from baseline falls within the equivalence margin (± 1.0)
- **Assumptions:** Normality and homogeneity of variance will be checked. If violated, non-parametric equivalent (e.g., **Wilcoxon rank-sum test**) will be used.
- **Secondary Endpoints:**
 - **Range of Motion (ROM) and Muscle Strength:**
 - **Test:** Repeated Measures ANOVA or mixed-effects model, depending on data completeness and correlation structure
 - If non-normal: **Friedman test** or **Wilcoxon signed-rank test** for within-group, **Kruskal-Wallis test** for between-group comparisons.
 - **Thermal Sensation, Comfort, and Acceptance (ASHRAE Scale):**
 - **Test:** Chi-square test or Fisher's exact test for categorical comparisons
 - **Ordinal regression** may be used to explore patterns of thermal perception across groups.
 - **Responding Analysis (pain reduction ≥ 3 points):**
 - **Test:** Chi-square test for group-wise comparison of response rates
 - **Risk difference** and **number needed to treat (NNT)** will be calculated.

Safety Analysis

- **Adverse Events (AEs) and Adverse Drug Reactions (ADRs):**
 - **Test:** Chi-square test or Fisher's exact test for comparing incidence across groups
 - Descriptive statistics for type, severity, onset, and duration
 - **Severity grading** and **causality assessment** using **Naranjo's algorithm**.
- **Rescue Medication Use:**
 - **Test:** Poisson regression or negative binomial regression if data are overdispersed
 - Summarized as a mean number of doses used per participant and compared between groups.

Demographic and Baseline Characteristics

- **Continuous Variables** (e.g., age, BMI):
 - **Test:** One-way ANOVA or **Kruskal-Wallis test** (if non-normal distribution)
- **Categorical Variables** (e.g., sex, diagnosis):
 - **Test:** Chi-square test or Fisher's exact test as appropriate

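### The protocol defines its primary endpoint as a BPI reduction of at least 3 points, but sizes and tests the trial on mean change within ±1.0

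*Protocol*

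**What the plan says.** All references are to the protocol.

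- **Definition.** Section 5.1: "The primary end-point is the difference of musculoskeletal pain reduction ≥ 3 scores". Section 7.9.1 says that a BPI difference of at least 3 "from initial scale of pain to the end of treatment will be captured as the primary efficacy endpoint".
- **Rationale for 3 points.** Section 5.1: "The selection of difference more than equal to 3 was chosen because if the participant has moderate pain at the beginning of the treatment", a fall to mild pain shows that treatment works. The same section bands scores as mild 1–3, moderate 4–6 and severe 7–10.
- **Sample size.** Section 6.7 takes a pain score as the outcome, with "Standard deviation (σ) : 1.81" and "Clinically meaningful margin (Δ or δ) : 1.0".
- **Primary analysis.** Under its primary endpoint heading, section 7.4.2 plans ANCOVA adjusted for baseline BPI and pairwise TOST "to assess whether the difference in mean change from baseline falls within the equivalence margin" of ±1.0.
- **The 3-point response.** Section 7.4.2 lists "Responding Analysis (pain reduction ≥ 3 points") under the secondary endpoints, with a chi-square test, risk difference and NNT. The four secondary endpoints in section 5.2 (safety, range of motion and muscle test, thermal scales, time to disappearance of pain) do not include it.
- **Instrument.** Section 7.9.1 names Form 2. That form has four 0–10 intensity items (worst, least, average, now) and seven 0–10 interference items. None is designated as the primary score.
- **Eligibility.** Section 6.2: "Patients diagnosed with musculoskeletal pain as described in the target population". Sections 6.1 to 6.3 set no minimum pain score.

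**The concern.** This is described as a Phase 3 confirmatory study whose objective (section 4) is to show equivalence. Such a trial needs one primary endpoint that is defined, powered and tested as the same quantity. Here the definition is a threshold on each participant's reduction, while the sample size and the test concern a difference between arm means.

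If the text stands, a reader of the results can point to 5.1 and ask for the responder comparison as the primary result. The protocol has no equivalence margin for that comparison and plans only a test of difference. A non-significant chi-square result does not show that response rates are equivalent.

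**Working it through.** **1. What the sample size was computed for.** Section 6.7 prints n = ((Z₁₋α/₂ + Z₁₋β) × σ/Δ)², with Z values 2.39 and 0.84, σ = 1.81 and Δ = 1.0, and reports 54 per group.

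- With the stated inputs: (3.23 × 1.81)² = 5.846² = 34.2, so 35 per group.
- The printed 54 comes from 4.059 in place of 3.23: (4.059 × 1.81)² = 53.98.

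That discrepancy is a separate matter, and nothing below depends on it. What counts here is that σ and Δ are both in points on a continuous scale. No response rate and no margin for a difference in proportions appears anywhere.

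**2. The statements side by side.**

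| Section | Quantity | Criterion |
|---|---|---|
| 5.1, 7.9.1 | Reduction of at least 3 points | Threshold, called primary |
| 6.7 | Pain score | SD 1.81, margin 1.0 |
| 7.4.2, primary | Mean change | TOST within ±1.0 |
| 7.4.2, secondary | Reduction of at least 3 points | Chi-square, no equivalence margin |

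The phrase in 5.1 might be read as a 3-point difference between groups. That does not help, because it would conflict with the 1.0 margin in 6.7 and 7.4.2.

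**3. How far apart the two endpoints can be.** Assume that changes are normal and that 1.81 is the SD of change. Then P(reduction ≥ 3) = Φ((μ − 3)/1.81) for mean reduction μ. Comparing arms with means μ and μ − 1:

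| μ | Responders at μ | Responders at μ − 1 | Difference |
|---|---|---|---|
| 2.0 | 0.290 | 0.135 | 0.156 |
| 2.5 | 0.391 | 0.204 | 0.188 |
| 3.0 | 0.500 | 0.290 | 0.210 |
| 3.5 | 0.609 | 0.391 | 0.218 |
| 4.0 | 0.710 | 0.500 | 0.210 |

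Differences are taken from unrounded values. A difference at the edge of the equivalence margin thus equals about 16 to 22 percentage points in responders.

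**4. Sensitivity to the SD.** Section 6.7 labels 1.81 as the SD of a pain score, not of a change. If it applies at both visits and the within-person correlation is ρ, the SD of change is 1.81 × √(2(1 − ρ)). This equals 1.81 at ρ = 0.5. In the extreme case ρ = 0 it is 1.81 × √2 = 2.56, and the largest responder difference (means 3.5 and 2.5) is 2Φ(0.5/2.56) − 1 = 0.155. The conversion shrinks but does not vanish.

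**5. The threshold and the bands.** A participant with baseline 1 or 2 can fall by at most 1 or 2 points and so cannot be a responder in any arm. The bands do not map onto 3 points exactly either: 7 to 4 is a 3-point fall that ends in moderate pain, and 4 to 3 reaches mild pain with a 1-point fall.

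**The case against.** **The statistical sections agree with each other.** Sections 6.7 and 7.4.2 both treat a continuous score, and 7.4.2 has one primary heading with the 3-point analysis placed under secondary. A reader might infer from 5.1 that two rival primary analyses are planned; the document does not support that. This part of the objection stands, and it shows which way to reconcile. It does not remove the contradiction: 5.1 and 7.9.1 both define the primary endpoint by the threshold, 5.1 gives a rationale for it, and 5.2 does not list it as secondary.

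**The unnamed item may be settled in a SAP.** This is fair. Form 2 and the visits are fixed, and the item could be named elsewhere, so it is a supporting point only.

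**Stronger readings that the documents do not support:**

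- *Floor-level participants will produce false equivalence.* The protocol gives no baseline distribution, no share of participants at the floor and no true difference, so no probability can be attached. If some enrolled participants have no room to improve, a smaller mean difference is also the true difference in the population that 6.1 and 6.2 define. It would be wrong only for a subgroup that the protocol does not name as its target.
- *The trial has a stated lack of power for the responder endpoint.* Any such figure needs a response rate and a proportion margin, and the protocol gives neither. It also plans no responder equivalence test.
- *A minimum baseline score is a necessary correction.* The rationale in 5.1 is conditional: it explains the threshold and does not define eligibility. Once the response is secondary, most of the reason for a minimum goes.

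**Conclusion.** The contradiction holds as written: the endpoint that 5.1 and 7.9.1 call primary is not the one that 6.7 sizes or that 7.4.2 tests as primary. It is a conflict between statements in the protocol itself, not a detail left for later.

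Its practical size is about 16 to 22 percentage points in 3-point responders at the edge of the ±1.0 margin. That rests on normal changes, an SD of change of 1.81 and mean reductions of 2 to 4. The conversion shows that the endpoints are not interchangeable; it does not predict what the arms will do.

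The absence of a minimum baseline score limits how the responder result can be interpreted, because participants starting at 1 or 2 count as non-responders whatever they receive. It is not an error in the primary analysis.

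**What to change.** - **5.1 and 7.9.1:** state one primary endpoint that matches 6.7 and 7.4.2, namely mean change from baseline to Visit 3 in one named Form 2 score, with pairwise equivalence tested by TOST within ±1.0. Which item or composite to use is the sponsor's choice, but it should be fixed before data are seen.
- **5.2:** add the 3-point response as a secondary endpoint, reported as a risk difference with a confidence interval. State that a non-significant chi-square test is not evidence of equivalence.
- **Interpretation:** note that participants with baseline 1 or 2 cannot meet the response criterion, and report how many there are per arm.
- **Optional:** a minimum baseline score on the same item is a design choice for the sponsor. It would make the responder result easier to read, but it would narrow the population and slow recruitment.

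The required changes are wording only. This point does not alter the margin, the test or the sample size. If the sponsor prefers the 3-point response as primary, the cost is much larger: 6.7 and 7.4.2 would need an assumed response rate, a justified margin for the difference in proportions, an equivalence test on that scale and a new sample size.
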